#### Antenatal

- Placenta praevia;
- Antepartum haemorrhage;
- Pregnancy-induced hypertension;
- PET/Pre-eclampsia/HELLP;
- Obstetric cholestasis;
- o Preterm pre-labour rupture of membranes;
- Gestational diabetes;
- Other significant complication

#### Intrapartum

- o Chorioamnionitis;
- Intrauterine growth restriction;
- Macrosomia;
- Infection

### Post-partum

Haemorrhage

The following outcomes will be assessed at 28 days post birth (or baby's discharge date from hospital whichever is sooner).

## Neonatal

- Congenital or chromosomal abnormalities;
- Admission to neonatal care unit;
- Early infection (as assessed by treating clinician);
- Retinopathy of prematurity;
- Necrotising enterocolitis;
- Intraventricular haemorrhage;
- Respiratory distress syndrome;
- Ventilation or oxygen support;
- Other significant complication

### **Patient reported outcomes**

- Health related quality of life (using the EQ-5D-5L questionnaire overall score and thermometer scale (36)) measured at baseline, during the first treatment cycle\* of IUI and/or IVF, and 19 months post randomisation (and 25 months for couples who conceive within 450 days of randomisation);
- Satisfaction with treatment and care provision (using the CSQ-8 (37)) measured during the first treatment cycle\* of IUI and/or IVF, and 19 months post randomisation (and 25 months for couples who conceive within 450 days of randomisation).

Consent will be taken from couples to allow longer-term assessment of pregnancy and live birth rate through routine data sources. Funding to carry out this work through to 5 years post-randomisation will be requested through a separate application.

\*The ideal timepoint during a treatment cycle to collect these questionnaires is between the date of insemination and the date of the pregnancy test for couples undergoing IUI, and between the date of embryo transfer and the date of the pregnancy test for couples undergoing IVF.

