# 2.2.5. Patient Reported Outcomes Objectives

- Health related quality of life (HRQoL) (using the EQ-5D-5L overall score and thermometer scale) measured at baseline, and 9 and 19 months post randomisation, plus 25 months for couples who conceive within 450 days of randomisation;
- Satisfaction with treatment and care provision (using the CSQ-8 [36]) post-treatment.

\_\_\_\_\_

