#### 8.2.2.2. Economic

The main outcome of the cost-effectiveness analysis is cost per live birth at ≥34 weeks gestation based on the principal outcome of the trial. Some secondary outcomes assessed in the trial including (HrQoL) in terms of quality-adjusted life-year (QALY) will also be reported and presented in the form of a cost-consequences analysis.

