# 9. TRIAL PROCEDURES

# 9.1. Schedule of assessments

**Table 2:** Schedule of Assessments

Trial process	Month 0	Month 2	Month 4	Month 6	Month 9	Month 19	Month 25	Ad hoc
Screening	Х							
Consent	Х							
Baseline data collection	Х							
Randomisation	Х							
IUI Treatment CRF		Х	Х	Х				
IVF Treatment CRF		Х			X 			
Laboratory CRF		Х	Х	Х	X 			
Frozen Transfer CRF		Х						
Clinical Pregnancy outcome						Χ	X 	X 
Post Treatment CRF						X 	X 	
EQ-5D-5L	Х	X 				Х	X 	
Health Resource use		X 				Χ	X 	
CSQ-8		X 				Χ	X 	
Complications - collected on Post Treatment CRF		х	х	х	х	x	X 	
Assessment of adverse events	Throu	ghout partic	ipant's time	on trial until	60 days after	the outcome	of the cycle is	known
Change of Status								Х
Protocol Deviations								Х
Non-trial treatment CRF								Х

Natural Pregnancy Notification					X 
Qualitative process evaluation	Х				
Qualitative bioethics				Х	

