## Additional notes on Error! Reference source not found.

- Months 2-6 are an approximation for when couples will have the three cycles of IUI; this process may be longer.
- X Couples randomised to IUI but progress to IVF as part of clinical care. All couples randomised to IUI cannot progress to subsequent IVF treatment until 270 days (approximately 9 months) post randomisation.
- X to measure outcomes for all couples who conceive within 450 days of randomisation.
- X³- one Clinical Pregnancy Outcome CRF to be completed per positive pregnancy test.
- X- to be completed for each pregnancy conceived during the trial outside of IVF or IUI treatment.
- X one Post-Treatment CRF to be completed 8 weeks after treatment starts (defined as the first day of ovarian stimulation).
- The qualitative sub-studies will approach participants at the indicated timepoints, but their interviews will happen in the subsequent weeks.
- X- measured during the first treatment cycle of IUI and/or IVF. The ideal timepoint during a treatment cycle to collect these questionnaires is between the date of insemination and the date of the pregnancy test for couples undergoing IUI, and between the date of embryo transfer and the date of the pregnancy test for couples undergoing IVF.

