11.2. Case Report Form (CRF) completion

The CRFs will include (but will NOT be limited to) the Forms shown in **Error! Reference source not found.** 

**Table 6**: Case report forms in UNiTY

Form Name	Schedule for submission
Informed Consent Form (one for each partner)	Prior to randomisation
Screening CRF	Prior to randomisation
Baseline CRF	Prior to randomisation
Baseline participant questionnaire: - EQ-5D-5L	Prior to randomisation
Treatment CRFs: - IVF treatment CRF - IUI treatment CRF - Laboratory CRF - Frozen Transfer CRF	During or as soon as possible after treatment
Outcomes CRF: - Post-treatment CRF	8 weeks after treatment starts (defined as the first day of ovarian stimulation) in order to capture all potential complications/outcomes.
Outcomes CRF: - Clinical Pregnancy outcome CRF	As soon as possible after each follow up assessment time point (19 months and 25 months post randomisation)
Outcome participant questionnaires  - EQ-5D-5L (one questionnaire to be completed for each partner)  - CSQ-8 (one questionnaire to be completed for each partner)  - Health resource use (one questionnaire to be completed per couple)	As soon as possible after each follow up assessment time point (during the first treatment cycle of IUI and/or IVF, 19 months and 25 months post randomisation)
Non-trial treatment form	During or as soon as possible after treatment
Natural pregnancy notification CRF	As soon as possible after becoming aware of participant's pregnancy
Serious Adverse Event Form	If expedited: emailed within 24 hours of site research team becoming aware of event If non-expedited: emailed within 4 weeks of site research team becoming aware of event
Change of Status Form	As soon as possible after the point of reduced participation
Deviation Form	As soon as possible after a protocol deviation has occurred

A CRF should be completed for each couple or individual participant as documented at the top of each document. CRFs repeat to account for multiple treatment cycles and multiple pregnancies.

In all cases it remains the responsibility of the PI to ensure that the CRF has been completed correctly and that the data are accurate. This will be evidenced by the signature of the PI, or delegate(s). The Site Signature & Delegation Log will identify all those personnel with responsibilities for data collection.

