#### 15.1. Economic data collection

The economic analysis will be conducted from the perspective of the health care system, accounting for the direct costs incurred by the UK NHS as recommended by NICE (42), including individual level data on all health-related resource use. The main resource categories that will be monitored include the following:

- 1. Drug administration
- 2. Resource use of standard care
- 3. Resource use associated with adverse events and complications (including premature birth and neonatal care)
- 4. Resource use associated with outpatient or emergency visits and hospital admissions
- 5. Contacts with community and social care services, such as general practitioner, practice nurse and counsellors

To estimate the overall cost of each trial-arm, unit costs will be applied and attached to each resource item. Information on unit costs will be obtained from centres participating in the trial and UK national sources such as NHS Reference Costs (39), Unit Costs of Health and Social Care (43), the British National Formulary (BNF), and Office for National Statistics (ONS). Costs used in other relevant published sources will be sought for use in sensitivity analysis.

HrQoL data will also be obtained based on participants' responses to the EQ-5D-5L. A preference-based index of HrQoL will be derived using the recently published English value set, and QALYs will be calculated using the area under the curve approach.

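### The 25-month EQ-5D-5L, CSQ-8 and resource-use questionnaires are limited to couples who conceive within 450 days, so comparing the arms on them at 25 months would compare selected subsets

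*Protocol*

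**What the plan says.** The protocol describes the 25-month questionnaires in four places, and these do not agree.

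- **Section 8.2.2.1, patient reported outcomes.** EQ-5D-5L and CSQ-8 are taken in the first treatment cycle (EQ-5D-5L also at baseline), "and 19 months post randomisation (and 25 months for couples who conceive within 450 days of randomisation").
- **Section 2.2.5.** EQ-5D-5L is "measured at baseline, and 9 and 19 months post randomisation, plus 25 months for couples who conceive within 450 days of randomisation". The restriction is the same, but there is a 9-month assessment and none in the first cycle. For CSQ-8 this section names only a post-treatment measurement.
- **Section 9.1, Table 2.** The 25-month cells for EQ-5D-5L, CSQ-8 and "Health Resource use" carry note X2, explained as "to measure outcomes for all couples who conceive within 450 days of randomisation". The 19-month cells carry no such note. There is no 9-month EQ-5D; the cell near month 2 refers to the first treatment cycle.
- **Section 11.2, Table 6.** The same three questionnaires are due "during the first treatment cycle of IUI and/or IVF, 19 months and 25 months post randomisation", with no condition on conception.

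On analysis, section 14.2 applies intention to treat to all outcomes. Section 14.2.2 names the CSQ-8 score among the continuous outcomes that receive an adjusted mean difference. Clinical objective 6 in section 2.2.1 is to compare couples' outcomes over 25 months. In section 15.1, "QALYs will be calculated using the area under the curve approach". Section 15.3 handles missing economic data by multiple imputation. No section says that the 25-month questionnaire data are descriptive or confined to conceivers.

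**The concern.** For a pregnancy-outcome form, asking only couples who conceived is natural. For quality of life, satisfaction and use of health services it is not. Conception by 450 days occurs after randomisation, and the two policies may produce it at different rates and in different kinds of couple. Once the sample is restricted to conceivers, randomisation no longer guarantees that the arms are comparable. The restricted comparison also leaves out any effect on quality of life that works through whether a couple conceives, which is probably the main route by which the policies could differ at that point.

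The loss is permanent. An analysis plan can choose a population or a model, but it cannot recover a questionnaire that was never sent.

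**Working it through.** **Step 1: the protocol's own figures.** Inputs from section 14.1: 28% in both arms, margin 10 points, one-sided alpha 0.025, power 90%, 10% loss.

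n per arm = 2 × 0.28 × 0.72 × (1.960 + 1.282)² / 0.10² = 423.66. Total = 2 × 423.66 / 0.90 = 941.5, which rounds up to the stated 942 (471 per arm). For 45% versus 35% at 25 months, power is 84.5% with 423 per arm and 88.1% with 471, in line with the stated figure of over 80%. The sample size is not in question; 471 per arm is the base for what follows.

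**Step 2: how many couples are not asked.** Number asked = 471 × conception rate by 450 days. The protocol gives no such rate. Its 45% versus 35% is an illustrative pair for live birth at 34 weeks or later. Conceptions include losses and so exceed such births, which is why higher rates are also shown.

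| Assumed conception by 450 days | Asked | Not asked | Share of 942 not asked |
|---|---|---|---|
| 45% vs 35% | 212 vs 165 | 259 vs 306 | 60% |
| 40% vs 40% | 188 vs 188 | 283 vs 283 | 60% |
| 55% vs 45% | 259 vs 212 | 212 vs 259 | 50% |

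At the ends of the range, 35% in both arms leaves 0.65 × 942 ≈ 612 couples unasked, and 55% in both arms leaves 0.45 × 942 ≈ 424.

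**Step 3: what selection can do to a difference.** The protocol gives no EQ-5D values, so gaps g of 0.02 to 0.10 are assumed, with 45% and 35% conceiving.

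- *Effect only through conception.* Conceivers score g above non-conceivers, equally in both arms. Among all randomised couples the difference is (0.45 − 0.35) × g = 0.002 to 0.010. Among conceivers it is 0, so the effect disappears.
- *No effect on any couple's score.* The extra 10% who conceive in only one arm score g below the other conceivers. The conceiver-only difference is −g × 0.10 / 0.45 = −0.004 to −0.022, so a difference appears where there is none.

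These values are small. They show that the error can run in either direction, not how large it will be.

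**Step 4: imputation.** Multiple imputation fills a gap from couples who resemble those with missing values and were observed. Here no non-conceiver has an observed 25-month value, so an imputed value would rest wholly on an assumption carried over from 19 months or from conceivers. The data could not test it.

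**Step 5: EQ-5D timing.** An area-under-the-curve QALY weights each score by the time between assessments. A score taken at 9 months and one taken between insemination or embryo transfer and the pregnancy test fall at different times and in different circumstances. Section 2.2.5 specifies the first; section 8.2.2.1 and Table 2 specify the second.

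**The case against.** The case against is that little depends on these data. Section 14.2 treats all secondary outcomes as exploratory. The explicit mention of 25 months in section 14.2.2 is attached to binary outcomes, and the CSQ-8 entry names no time point. Section 15.3 reports QALYs separately and does not anticipate cost per QALY. The horizon for these measures could be left to the statistical or health economics analysis plan. Most of this stands, and it keeps the point at the level of secondary outcomes. It does not answer who is sent the form: the protocol fixes that, and fixes it inconsistently.

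A reader might infer more than the documents support.

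- *That non-conceivers have no cost data to 25 months.* The treatment forms and the non-trial treatment form in Table 2 carry no condition on conception. Section 1.1.4 records IVF after IUI up to 25 months, and section 7.1.2 collects outcomes of further frozen transfers over the same period. Only the resource-use questionnaire is withheld.
- *That QALYs cannot be computed for non-conceivers.* Section 8.2.2.1 and Table 2 schedule EQ-5D at baseline, first cycle and 19 months whether or not a couple conceives, so QALYs to 19 months are available in principle. No section sets a 25-month QALY or cost horizon.
- *That the main economic result is distorted.* That result is "cost per live birth at ≥34 weeks gestation based on the principal outcome of the trial", assessed at 19 months. Section 15.2 anticipates crossover to IVF and considers a model for it. No section says that costs of IVF after day 270 will be set only against births conceived by day 270.
- *That the data are conditioned on the primary outcome.* The condition is conception within 450 days. The primary outcome is live birth at 34 weeks or later, conceived within 270 days.

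The restriction on resource use also rests on note X2 alone, which states a purpose rather than an exclusion. That is a further reason to make the wording explicit.

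**Conclusion.** The point holds in a limited form. Read as written in sections 2.2.5 (EQ-5D only), 8.2.2.1 and 9.1, the protocol withholds the 25-month EQ-5D-5L, CSQ-8 and resource-use questionnaires from couples who have not conceived by 450 days. Section 11.2 shows no such limit, and the intention-to-treat statement in section 14.2 cannot be met for these measures at 25 months. A between-arm comparison at that time would be selected, and imputation could not correct it from the data.

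About 45% to 65% of couples would lack a 25-month questionnaire by design, on the assumption that 35% to 55% conceive by 450 days. Comparisons to 19 months, clinical pregnancy outcomes and fertility-treatment costs recorded on case report forms are not affected. The conflict over EQ-5D timing is separate and plain on the text. Both should be corrected while forms can still be sent.

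**What to change.** Choose one of two courses.

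1. **Ask everyone.** Send the 25-month EQ-5D-5L, CSQ-8 and resource-use questionnaires to all couples and remove the conception condition for these three rows of Table 2. The cost is extra questionnaires, some to couples who may find them burdensome after unsuccessful treatment.
2. **Limit the comparison.** Keep the restriction, but state that between-arm comparisons of EQ-5D, CSQ-8, QALYs and questionnaire-based resource use stop at 19 months, and that 25-month data from conceivers are descriptive. This costs only wording, but it gives up any randomised comparison of these measures at 25 months.

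Under either course, make sections 2.2.5, 8.2.2.1, 9.1 (Table 2 and note X2) and 11.2 (Table 6) agree on who is asked at 25 months, and on whether EQ-5D is taken at 9 months or during the first treatment cycle. State the resulting assessment times in section 15.1, since the QALY calculation depends on them. This too is wording only.

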#### 8.2.2.2. Economic

The main outcome of the cost-effectiveness analysis is cost per live birth at ≥34 weeks gestation based on the principal outcome of the trial. Some secondary outcomes assessed in the trial including (HrQoL) in terms of quality-adjusted life-year (QALY) will also be reported and presented in the form of a cost-consequences analysis.

#### 8.2.2.3. Healthcare science outcomes

The healthcare science outcomes are covered in the Sub-Study section (see Section 16.2). The following outcomes will be assessed:

- Healthcare science characterisation of the standardisation of sperm analysis results.
- Measurement of prognostic value of existing sperm analysis markers for both IUI and IVF.
- Novel sperm flagellar markers with prognostic value for both IUI and IVF.

### 8.2.2.4. Bioethics

The aims of the bioethics sub study are:

- To explore the perceptions of participants, fertility professionals (e.g. doctors, nurses, clinic staff) and service commissioners around access to fertility treatment.
- To gain greater understanding of how the priorities of service providers intersect with patients' perspectives (e.g. commissioners might prioritise low-cost treatment, while for couples having a pregnancy/child might be a higher priority)
- To improve access to trials in this area and understand how funding restrictions could impact on trial participation.

# 9. TRIAL PROCEDURES

# 9.1. Schedule of assessments

**Table 2:** Schedule of Assessments

Trial process	Month 0	Month 2	Month 4	Month 6	Month 9	Month 19	Month 25	Ad hoc
Screening	Х							
Consent	Х							
Baseline data collection	Х							
Randomisation	Х							
IUI Treatment CRF		Х	Х	Х				
IVF Treatment CRF		Х			X 			
Laboratory CRF		Х	Х	Х	X 			
Frozen Transfer CRF		Х						
Clinical Pregnancy outcome						Χ	X 	X 
Post Treatment CRF						X 	X 	
EQ-5D-5L	Х	X 				Х	X 	
Health Resource use		X 				Χ	X 	
CSQ-8		X 				Χ	X 	
Complications - collected on Post Treatment CRF		х	х	х	х	x	X 	
Assessment of adverse events	Throu	ghout partic	ipant's time	on trial until	60 days after	the outcome	of the cycle is	known
Change of Status								Х
Protocol Deviations								Х
Non-trial treatment CRF								Х

Natural Pregnancy Notification					X 
Qualitative process evaluation	Х				
Qualitative bioethics				Х	

## Additional notes on Error! Reference source not found.

- Months 2-6 are an approximation for when couples will have the three cycles of IUI; this process may be longer.
- X Couples randomised to IUI but progress to IVF as part of clinical care. All couples randomised to IUI cannot progress to subsequent IVF treatment until 270 days (approximately 9 months) post randomisation.
- X to measure outcomes for all couples who conceive within 450 days of randomisation.
- X³- one Clinical Pregnancy Outcome CRF to be completed per positive pregnancy test.
- X- to be completed for each pregnancy conceived during the trial outside of IVF or IUI treatment.
- X one Post-Treatment CRF to be completed 8 weeks after treatment starts (defined as the first day of ovarian stimulation).
- The qualitative sub-studies will approach participants at the indicated timepoints, but their interviews will happen in the subsequent weeks.
- X- measured during the first treatment cycle of IUI and/or IVF. The ideal timepoint during a treatment cycle to collect these questionnaires is between the date of insemination and the date of the pregnancy test for couples undergoing IUI, and between the date of embryo transfer and the date of the pregnancy test for couples undergoing IVF.

## 9.2. Withdrawal and changes in levels of participation

Informed consent is defined as the process of learning the key facts about a clinical trial before deciding whether or not to participate. It is a continuous and dynamic process and participants should be asked about their ongoing willingness to continue participation at all visits. Participants should be aware from the beginning that they can freely withdraw (cease to participate) from the trial at any time. A participant may wish to cease to participate in a particular aspect of the trial without completely withdrawing. Couples who have decided not to adhere to their randomisation treatment allocation but are willing to be followed up in accordance with the schedule of assessments should not be treated as withdrawals. In this instance a protocol deviation form should be completed.

The changes in levels of participation within the trial are categorised in the following ways:

Partial withdrawal - One or both partners wish to withdraw from certain aspects of the trial, such as the intervention, follow-up, completion of questionnaires and/or data collection.

Complete withdrawal - No further data collection: The couple are not willing to be followed up in any way for the purposes of the trial AND do not wish for any further data to be collected (i.e., only data collected prior to any changes of levels in participation can be used in the trial analysis).

Withdrawal from one of the sub-studies: Participants may withdraw from the QPE and/or the Bioethics Sub-study within 2 weeks of the data collection event but may still continue in the main trial. It is not possible to withdraw from the Healthcare science outcomes sub-study as this is mandatory for trial participation.

The details of changes in levels of participation in the trial (date, reason and category of status change) should be clearly documented in the participant's medical notes and captured on the Change of Status CRF. All withdrawals should be discussed with the UNITY trial office before completing the CRF.

Participants found to be ineligible post-randomisation should be followed up according to all trial processes and a protocol deviation CRF should be completed.

Further information about withdrawal from the qualitative process evaluation and bioethics study can be found in section 16.

